### **VHA providers: Eligibility, recruitment, and procedures.**

There will be at least 2-4 VA providers at each of the two sites (n=4-8 total), and following the discontinuation of the VA Connecticut-West Haven Site, there will be at least 2-4 VA providers at VA Boston. Various types of providers will be included (e.g. psychologists, social workers). Providers will participate in training on RISE and the information/referral condition, providers will audiotape their sessions and participate in weekly consultation. Providers will also have the option to enroll and participate in a 30-minute phone interview near the end of the RCT in order to help us learn about the acceptability and feasibility of implementing RISE in VA, including barriers and facilitators to RISE implementation and completion of two brief quantitative measures regarding the perceptions of the intervention and its implementation (“described under Measures”). These interviews will be brief (approximately 30 minutes), audio recorded, and administered by a trained/qualified Project Manager, PI ([name]) or Research Assistant via telephone. The interviews will be recorded and transcribed. We recognize that VA employees are a vulnerable population and will take special care to ensure that participants understand that their participation is completely voluntary and will not affect their VA employment in any way (see additional details under Potential Risks and Adequacy of Protection Against Risk). VA providers can be of any gender, age, and racial/ethnic background.

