### RISE Background and Theoretical Basis:

RISE is a promising and innovative intervention for IPV. The PI, who has 14 years of clinical specialization in IPV, developed RISE based on her HSR&D CDA findings in conjunction with two national experts in women's primary care and behavioral health, Drs. [name] and [name] (Co-Is). RISE was developed using rigorous methods, including extensive literature review, as well as focus groups and surveys with WVs who experienced IPV and qualitative interviews with VA providers. It was subsequently piloted successfully in clinical practice. RISE is a primary care-based trauma-informed psychosocial intervention for female patients who experience IPV. RISE is designed to overcome the limitations of existing brief interventions for IPV. It is variable-length and consists of an initial session of up to 60 minutes, with up to 5 additional 60-minute sessions (i.e., up to 6 sessions total). This format is consistent with brief counseling standards established for Primary Care Mental Health Integration (PC-MHI) (VHA Handbook 1160.01). Many VA primary care clinics have implemented PC-MHI, which may be ideal for implementing RISE (personal communication, [name], WHS Deputy Chief Consultant, June 10, 2015). VHA also recommends that all VAMCs designate domestic violence coordinators (DVCs) who provide education to clinicians, connect patients with IPV-related resources, and provide some clinical care. A strength of RISE is that it can be delivered by various providers within primary care (e.g., PC-MHI providers, nurses, social workers) or by providers closely aligned with primary care. This flexibility accommodates the realities of real world practice, including the limited clinical role of many DVCs.

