#### Delivery of RISE:

RISE includes the essential components of prior brief counseling interventions for IPV but provides a more comprehensive and individualized approach to improving women's health and safety. In the initial session, women are offered safety planning tips and a resource list. Women are then given a menu of options to select from based on their current needs and preferences. For example, a woman may choose to focus on safety planning in detail or she may select coping skills/self-care to better manage stress. The principles of empowerment and flexibility undergird the format. The patient can choose to focus on the same module in her next session or select a new module. This pattern is repeated for up to 6 sessions or when the woman no longer needs or desires further intervention, consistent with brief counseling standards (VHA Handbook 1160.01). In the latter case, it is a collaborative decision made between the patient and provider. An important feature of RISE is laying the groundwork for necessary referrals (e.g., to mental health) that women are offered during and upon completion of RISE. Given the current state of the pandemic, COVID-19, we are requesting to deliver RISE via teletherapy (phone) and videoconferencing using VA-approved platforms (e.g., VVC). More specifically, we are requesting that the PI ([name]) the two RISE providers on the study, Drs. [name] and [name], who are both licensed clinical psychologists, be able to conduct RISE sessions from their homes via telephone, with adherence to VVC requirements. In order to ensure participant safety when conducting teletherapy or videoconferencing, providers will confirm the participant's address and phone number at the beginning of the call and follow usual clinical guidance for managing any emergent SI or other risk issues, as we would in routine care. We will ensure the participant is in a safe place where she can speak freely. With participant permission in advance of the session, we will send RISE resources and handouts as well as our in-session measures, which we will collect at the beginning of the session via teletherapy. While teleworking RISE providers have full access to CPRS, suicide coordinators, and have access to clinical resources, such that providers are able to address any emergent concerns that arise for participants. As such this delivery modality does not pose any increased risk to participants or study providers, and is in accordance with recommended precautions and procedures of social distancing during this unprecedeted time.

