**RISE.** The RISE will be delivered as per the refined manual, with its variable-length format (1 to up to 6 sessions within an approximate 10 week period). Following completion of the initial 60-minute RISE session, the provider and participant will determine whether they will have an additional session, and if so, it will be scheduled. Because RISE is specifically designed to be variable-length and patient-centered, it is possible that a participant may only desire to have 1 RISE session. Based on patient and provider feedback during Phase 2, all 6 of the RISE sessions can be up to 60 minutes. Originally, the subsequent sessions were intended to be 30-40 minutes, but that has proved infeasible. Both patients and providers have suggested that more time is allotted for subsequent sessions. Participants may have up to 6 RISE sessions in total. Intervention sessions will occur in private office space within primary care and/or mental health (e.g., Women’s Division of the National Center for PTSD). During times of unforeseen circumstances, such as the COVID-19 public health crisis of 2020, the clinical research sessions will be offered in telehealth format from the homes of licensed clinical psychologists [name] and [name], ensuring safe and private conditions for both the interventionists and the participants by following VA Boston’s and national VVC guidance for such clinical care. Individuals in the RISE condition will also complete the four brief validated self-report measures of empowerment, self-efficacy, patient activation, and valued action at the beginning of each RISE session to gauge treatment progress in real time and guide module selection, as we have done in Phase 2. Note these measures will be collected by the interventionist over the phone for any telehealth visits. This process takes approximately 10 minutes (leaving approximately 50 minutes for the RISE session). Participants will initially be emailed RISE intervention materials following their consenting/enrollment session, after which they will have the option to receive RISE intervention materials via USPS mail.

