The study will incorporate a 2 x 3 (Condition: RISE vs. information/referral x Time: pretreatment, post, and 1-month follow-up) mixed-factorial multi-measurement design producing  $N=60 \times 3$  time points = 180 measurement observations (or up to  $N=68 \times 3$  timepoints = 204). The intervention in this study is a difference over and above standard care (not in isolation), so it is expected that the effect will be modest ( $d=.5$ ,  $f^2=.15$ ,  $PV=.1$ ). Traditional approaches to repeated measures can thus be used to assess power. However, the design affords two alternate methods. The interaction term from the multilevel model will have 118 degrees of freedom, given the study design, which is more than sufficient to render a power = .95 for the primary outcomes. A simulation was also conducted leveraging the inputs from the prior studies, assuming a modest effect size, to determine power. In all simulated conditions, power is estimated  $>.80$  for primary outcomes. Consistent with the American Statistical Association recommendations, we will examine effect sizes and 95% confidence intervals, along with p-values in our tests.

We will assess the feasibility and acceptability of RISE and the comparison condition by looking for consistent patterns in rates of intervention attendance (i.e., number of RISE sessions attended) and reasons for RISE termination. We will examine the acceptability of both interventions using data from the CSQ-8 and qualitative data from patient interviews. Provider quantitative measures of feasibility and acceptability will be primarily

descriptive in nature, including mean summary scores and proportion of participants rating the intervention as feasible and acceptable. Lower scores will indicate a need to examine a given dimension more closely. We will integrate qualitative analyses within the quantitative analyses for the purposes of expansion, development, and convergence.

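### The PI, who developed RISE, may interview the providers about RISE and possibly deliver it too, so the provider findings for sub-aim 3a are at risk of bias towards RISE

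*Combined protocol and SAP*

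**What the plan says.** Sub-aim 3a (*Specific Aims for Phase 3 Research*) is to evaluate the feasibility and acceptability of RISE within the RCT. The *Randomized clinical trial (RCT)* paragraph presents the provider interviews as a means to that sub-aim.

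*VHA providers: Eligibility, recruitment, and procedures* sets out the provider component:

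- After the second site was dropped, "there will be at least 2-4 VA providers at VA Boston".
- Taking part is optional: "Providers will also have the option to enroll and participate in a 30-minute phone interview near the end of the RCT". The interview covers acceptability, feasibility, barriers and facilitators, and two short quantitative measures go with it.
- The interviews are "administered by a trained/qualified Project Manager, PI ([name]) or Research Assistant via telephone".

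*RISE Background and Theoretical Basis* identifies the developer: "The PI, who has 14 years of clinical specialization in IPV, developed RISE based on her HSR&D CDA findings", together with two co-investigators.

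*Delivery of RISE* contains a telehealth request for the pandemic: "we are requesting that the PI ([name]) the two RISE providers on the study" be able to hold RISE sessions from home.

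*Quantitative Data Analyses (Aim 3)* summarises the provider measures descriptively, by mean scores and the "proportion of participants rating the intervention as feasible and acceptable".

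**The concern.** A provider asked about the faults of an intervention by the person who created it, and who leads the study, has a reason to soften the answer. A developer who rates the intervention brings allegiance to it. Both pressures plausibly act in one direction, towards RISE.

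This matters because *Innovative Design* justifies the Hybrid 1 design by early collection of implementation data, which is useful only if providers report barriers candidly. The provider evidence before the trial also came through the developers: *Development of RISE* describes piloting in their own clinical work and an informal survey of providers. The RCT is the opportunity to obtain provider evidence at a greater distance from them.

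**Working it through.** The plan gives no figure to reproduce. The check is mainly a comparison of texts, with one conditional calculation.

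**Step 1: who may interview.** The provider section permits three roles: project manager, PI or research assistant. The PI's permission is explicit.

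**Step 2: whether the PI is a developer.** Yes, according to *Rationale*, where the PI is credited with developing RISE, and to *RISE Background and Theoretical Basis*.

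**Step 3: whether the PI may deliver RISE.** The sentence in *Delivery of RISE* lacks a word or punctuation between the PI and the two RISE providers. It can be read as the PI plus two others. The RISE paragraph under *Randomization and intervention delivery* refers only to two home-based psychologists, with names masked. The provider section gives a number but does not say who. These three places do not settle whether the PI is one of the providers.

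**Step 4: whether a safeguard acts at the interview.**

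- Voluntary participation (provider section) protects employment, not candour towards the developer.
- The semi-structured format (RCT paragraph) fixes the topics, not who asks.
- Recording and transcription (provider section) keep what was said.
- Structured templates and double coding of 20% of transcripts (*Qualitative Data Analyses (Aim 3)*) act afterwards and cannot recover criticism that was never voiced.

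Nothing visible requires a non-developer interviewer or separate reporting of a developer's ratings.

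**Step 5: weight of one developer among the respondents.** Assume that one developer delivers RISE, opts in and rates it favourably. Let n be the number of respondents including the developer, and k the number of favourable ratings among the other n − 1.

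- Proportion with the developer: (k + 1)/n
- Proportion without: k/(n − 1)
- Shift: (k + 1)/n − k/(n − 1) = (n − 1 − k)/[n(n − 1)]

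With k = 0 the shift is 1/n. With k = n − 1 it is 0.

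| n | k | With | Without | Shift (points) |
|---|---|---|---|---|
| 2 | 0 | 50% | 0% | 50 |
| 2 | 1 | 100% | 100% | 0 |
| 3 | 0 | 33% | 0% | 33 |
| 3 | 1 | 67% | 50% | 17 |
| 3 | 2 | 100% | 100% | 0 |
| 4 | 0 | 25% | 0% | 25 |
| 4 | 1 | 50% | 33% | 17 |
| 4 | 2 | 75% | 67% | 8 |
| 4 | 3 | 100% | 100% | 0 |

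The provider count is given as a minimum, so n may exceed 4, and the largest possible shift would then be below 25 points.

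**Step 6: the interviewer effect.** The documents give nothing from which to estimate how far answers change when the PI asks the questions. No figure is offered.

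**The case against.** The strongest case on the other side is that everything here is conditional. The PI is one of three permitted interviewers and may conduct none of the interviews. The reading that the PI delivers RISE depends on a garbled sentence about pandemic telehealth. Delivering a session does not make someone a research respondent, because the interview is opt-in. The provider section also refers to a section on risks and protections, and to descriptions of the provider measures, that are not in the available text; safeguards may stand there. The provider ratings are descriptive, with no test or threshold, and sub-aim 3a also draws on attendance, reasons for termination, the CSQ-8 and patient interviews. *Subjects and generalizability* concedes that the findings will not be definitive.

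Most of this stands, and it limits what can be claimed. A reader might infer three stronger things that the documents do not support:

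- **That the provider result is biased.** The text shows that a conflict is permitted, not that it will occur.
- **That the PI will rate RISE as a respondent.** No text says so; there is only no rule against it.
- **That the distortion is 25 to 50 points.** Those are maxima under the assumptions of step 5, and the shift is zero if the other providers are all favourable.

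The objection does not remove the written permission for the developer to interview. Even if an unseen section asks for an independent interviewer, the sentence in the provider section would have to be brought into line with it.

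**Conclusion.** The point holds as a risk in the provider component of sub-aim 3a, and is worth correcting because the correction is cheap. The interviewer half rests on explicit text. The respondent half is conditional on three things: that the PI or a co-developer delivers RISE, opts in, and rates it favourably when others do not.

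The direction, towards RISE, is a judgement from the roles involved. The interviewer effect has no computable size. The respondent effect lies between 0 and 1/n. Aim 3's randomised comparison, attendance and the CSQ-8 are outside the concern.

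**What to change.** 1. In *VHA providers: Eligibility, recruitment, and procedures*, delete the PI from the list of interviewers. The project manager or research assistant then conducts every provider interview and collects the two provider measures.
2. In *Quantitative Data Analyses (Aim 3)*, state that if the PI or a co-developer delivers RISE and opts in, those ratings are listed separately from the provider means and proportions.
3. Reconcile *Delivery of RISE*, the RISE paragraph under *Randomization and intervention delivery*, and the provider section on who delivers RISE.

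No new staff are needed, since both alternative interviewers are already named, and the interviews come late in the trial. The cost is less expert probing and possibly one fewer rating in the pooled summary; separate listing loses no data. The remaining interviewers are also study staff, so the change reduces the pressure without removing it.

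A promise that the PI sees only de-identified summaries is not recommended. With perhaps 2 to 4 providers in weekly consultation, identities would be easy to guess. *Qualitative Data Analyses (Aim 3)* also gives oversight of all qualitative work to an investigator whose name is masked and who may be the PI.

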### **Measures**

#### **For Women VA Patient Participants:**

Demographics: A brief measure of background information (e.g., age, race, sexual orientation, relationship status, number of deployments, housing status). Background information surrounding age, race, sexual orientation, and number of deployments will be collected at Pre, while demographic information on relationship status and housing status will be collected at all three timepoints (table 4).

Personal Progress Scale – Revised: A measure of empowerment in women, demonstrating excellent reliability and validity in diverse sample of women.

General Self-efficacy Scale (GSS)65a: A reliable and valid 10-item scale that is designed to assess optimistic self-beliefs to cope with a variety of difficult demands in life.

Patient Activation Measure-Short Form (PAM-13)65b: A brief validated measure of patient activation including: patient knowledge, skill, and confidence for self-management. The 13-item abbreviated measure has psychometric properties similar to the original 22-item version.

Valued Living Questionnaire (VLQ): The VLQ is a two-part questionnaire that measures (a) the importance of 10 valued areas of living, and (b) the extent to which one's actions are consistent with one's values. For each domain (e.g., family, physical self-care, friends/social life), respondents use a 1–10 scale to rate how important each value is to them and how consistently they have lived in accordance with this value over the past week. Responses from both importance and consistency are multiplied to derive a value composite score.

Center for Epidemiologic Studies – Depression Scale (CES-D): The CES-D is a psychometrically sound and widely-used 20-item questionnaire designed to measure the frequency of past-week depressive symptoms. It is sensitive to change over relatively short periods of time.

Health Service Use (HSU): Assesses VA and non-VA health service use using a modified version of [name] health service use (HSU) measure. This measure has been used in prior studies by [name] (HSR&D IIR 12-345) and has been modified slightly for the purposes of this study. This will allow us to examine whether RISE leads to increased access and engagement with relevant health services.

The Conflict Tactics Scale-Revised (CTS-2): is a 39-item, behaviorally specific measure of intimate partner conflict, including physical, sexual, and psychological IPV. This measure has strong psychometric properties and is the most commonly-used measure of IPV. This measure will be used to assess the scope of past-year IPV experiences in this sample.

PTSD Checklist for DSM-5 (PCL-5): The PCL-5 assesses the 20 DSM-5 symptoms of posttraumatic stress disorder.

15-item Patient Health Questionnaire (PHQ-15): The PHQ-15 assesses somatic symptoms by asking patients whether symptoms are present and the extent of their severity on a scale from 1 (not bothered at all) to 3 (bothered a lot).

12-item Short Form Survey (SF-12): The SF-12 assesses health-related quality of life with questions regarding patients' abilities to perform their usual activities. The measure includes two subscales for physical and mental health.

Safety Behaviors Checklist (SBC): The SBC assesses patients' behaviors to safeguard themselves against intimate partner violence and plan escape from an intimate partner, including such items as "Have you ever hidden money?" and "Do you have a hidden bag with extra clothing available?"

Connor-Davidson Resilience Scale (CD-RISC 25): The CD-RISC 25 is a validated self-report measure of resilience (Campbell-Sills & Stein, 2007). Items include statements about one's response to stress in the domains of control, commitment, hardiness, goal-orientation, self-esteem, adaptability, social skills, humor, strengthening through stress, and endurance of pain. Participants were asked to rate their level of agreement on a 5-point Likert scale from "*not true at all*" to "*true nearly all the time*" to items such as "I am able to adapt when changes occur." The summed resilience scores range from 0-40, with higher scores indicating greater resilience. The CD-RISC 25 is considered a high-quality resilience scale with acceptable psychometric support (Windle, Bennett, & Noyes, 2011). This measure has been used both in studies that conceptualize resilience as a stable, within-person trait, and as a modifiable construct.

Client Satisfaction Questionnaire-8 (CSQ-8): The CSQ-8 evaluates patients' satisfaction with the service they received (i.e., RISE or the information/referral), with items including "How satisfied are you with the amount of help you have received?" and "If you were to seek help again, would you come back to our program?" (post-treatment and 1 month follow-up only).

Depression Anxiety Stress Scale (DASS) (DASS-Anxiety Subscale): The anxiety subscale contains 14 items which assess autonomic, skeletal muscle effects, situational anxiety, and subjective experiences of anxious affect. 4-point severity/frequency scales are used and summed. The DASS has been shown to have high internal consistency and yield meaningful discriminations in a variety of settings (Lovibond & Lovibond, 1995).

Coping Strategy Inventory- Short Form (CSI-SF) : The CSI-SF was structured to reflect the original CSI scale, with four 4- item subscales: (a) Problem-Focused Engagement, (b) Problem-Focused Disengagement, (c) Emotion-Focused Engagement, and (d) Emotion-Focused Disengagement. Respondents were asked to rate the general frequency with which they utilize each listed coping strategy on the survey and to indicate their choices in the following manner: 1 = "Never", 2 = "Seldom", 3 = "Sometimes", 4 = "Often" and 5 = "Almost Always". Individuals receive scores for each first-tier subscale (Engagement vs. Disengagement: range = 8 – 40), as well as for each of the four second tier subscales (Problem-Focused Engagement, Problem-Focused Disengagement, Emotion-Focused Engagement, and Emotion-Focused Disengagement: range = 4 – 20). Each of the four 2nd tier subscales created contained four items each. The CSI-SF demonstrates reliability and validity.

Acceptability: Brief qualitative and semi-structured interview questions assess patients' perceptions of the feasibility and acceptability of their respective intervention (post-treatment and 1-month follow-up only).

Military sexual trauma (MST): MST will be measured with the two following dichotomous (yes/no) VA clinical reminder items: "When you were in the military... a) did you ever receive unwanted, threatening, or repeated sexual attention (for example, touching, cornering, pressure for sexual favors, or inappropriate verbal remarks, etc.); b) did you have sexual contact against your will or when you were unable to say no (for example, after being forced or threatened or to avoid other consequences)?" Evaluation of these items against

clinical interview yielded a sensitivity of .92 and specificity of .89 for the first question and a sensitivity of .89 and specificity of .90 for the second question (McIntyre et al., 1999).

Combat exposure: We developed a single dichotomous (yes/no) item to assess exposure to combat: “During any of your deployments, did you have any exposure to combat (for example, you fired a weapon, were under fire, or saw people who were injured or killed in battle)?” Only those participants who indicate that they have been deployed will be prompted to complete this question.

IPV-Related Head Injury: We adapted the VA-DoD TBI screener to assess a history of IPV-related head injuries, probable TBI history, and TBI-related sequelae (Donnelly et al., 2011). Because concussion is a relatively common consequence of IPV to the face or head. We would like to assess whether IPV-related TBI history, with or without current symptoms, attenuates the effectiveness of treatment. It may be an important area to address as part of counseling for women who have experienced IPV. This 4-item screener allows us to determine probable IPV-related TBI history, with and without current symptoms. Studies using this measure suggests its utility in determining IPV-related TBI history among a sample of women Veterans (e.g., [name] & Pogoda, 2015).

